4.5.2.1. Adverse Events of Special Interest

The following AEs of special interest will be reported:

- ALT increase
- Vascular inflammation and complement activation
- Thrombocytopenia
- Renal injury

An up-to-date list of specific MedDRA Queries (SMQs), high level terms (HLTs) or individual preferred terms (PTs) used to identify adverse events of special interest (AESIs) is periodically updated and stored in a central location. At the time of database lock, the latest version of the terms will be extracted and used to identify AESIs.

All AEs of special interest will be summarized by SOC and PT, and, also summarized by SOC, PT and maximum grade. Serious AESIs will be summarized by SOC and PT. All AEs of special interest will be listed.

Separate outputs will be created for each AESI category (ALT increase, vascular inflammation and complement activation, thrombocytopenia, renal injury) to explore the data in more detail if data permits.

Event Characteristics: The characteristics of all event occurrences during the post-baseline period will be summarized, which looks at event characteristics (serious, drug-related, leading to withdrawal, severe or Grade 3-4, fatal), number of events per participant, outcome, maximum grade or intensity and action taken.

4.5.2.2. COVID-19 Assessment and COVID-19 AEs

A standardized MedDRA Query (SMQ) will be used to identify all COVID-19 AEs.

The overall incidence of AEs and SAEs of COVID-19, COVID-19 AEs leading to study intervention discontinuation, COVID-19 AEs leading to study withdrawal, and Grade 3 and 4 COVID-19 AEs / severe COVID-19 AEs will be summarized. The incidence of these events at individual PT level can be obtained from the standard AE/SAE summaries.

COVID-19 assessments for participants with potential, suspected or confirmed COVID-19 AEs will be summarized.

If >5% participants overall report ≥ 1 COVID-19 AE, then onset and duration of the first occurrence of COVID-19 AEs, and COVID-19 AE symptoms (from the COVID-19 eCRF page) will be summarized. The same rule will apply to COVID-19 SAEs.

4.5.2.3. Impact of COVID-19 Pandemic on Safety Results

The impact of the COVID-19 pandemic on the safety results will be assessed. Pandemic measures began in different countries at different times. A dataset containing the date when pandemic measures began, as determined by the GSK country Issue Management Teams

(IMT), will be used to determine the start date of each wave of pandemic measures within each country.

Summaries of the incidence rates of AEs, SAEs, and Grade 3 and 4 AEs / severe AEs, before (AE onset date < pandemic measure start date) and after (AE onset date \geq pandemic measure start date) the start of the COVID-19 pandemic will be produced, overall and by country/region, gender, and age group.

4.5.3. Additional Safety Assessments

4.5.3.1. Laboratory Data

Only central lab data will be used for summary analyses and figures; local lab data will be included in listings, as appropriate.

If normal LAB ranges are collected and there are duplicate LAB records at the same date/timepoint, the “worst-case” value will be selected. Specifically:

- For LAB result > Lower Normal range, select Maximum of Lab result (AVAL).
- For LAB result \leq Lower Normal range, select minimum of Lab result (AVAL).

For virology LAB parameters, if time information is missing from collection and from the test performed, the maximum lab value should be selected. If first run has values outside acceptance criteria, and the sample was re-run, the latest LAB result should be selected by the vendor.

Summary statistics for changes from baseline for each numeric parameter at each visit will be presented, separately for all clinical chemistry parameters, all haematology parameters, and all urinalysis parameters.

For immunology parameters, summary statistics for actual value and change from baseline data for each parameter at each visit will be presented, separately for all numeric parameters. Listings will also be created.

For categorical immunology parameters c-ANCA and p-ANCA, summary table of baseline Negative to post-baseline Positive, baseline value no change, and baseline Positive to post-baseline Negative will be created. Listing will be created as well.

For coagulation parameters prothrombin international normalised ratio (INR), prothrombin time (PT_{test}) and activated partial thromboplastin time (aPTT), summary statistics for actual at each visit will be presented. Listing will be created as well.

Shift tables for laboratory parameters showing baseline toxicity versus maximum post-baseline (on-treatment and off-treatment periods combined) toxicity for each grade (Grade1, Grade 2, etc.) for chemistry and haematology parameters will be provided.

Increase to Grade 3 or higher lab abnormalities for platelets, ALT, aspartate aminotransferase (AST), INR, total bilirubin, serum creatinine, eGFR, albumin to creatinine ratio (ACR) will be summarized.

Laboratory values outside of normal range will be summarized and listed.

Grading categories for laboratory tests are determined using the DAIDS grading system Version 2.1 [[National Institute of Allergy and Infectious Diseases. Division of AIDS, 2017](#)].

Summary of post-baseline hepatobiliary laboratory abnormalities will be provided.

The worst-case urinalysis results post-baseline (on-treatment and off-treatment periods combined) relative to baseline will be summarized.

Summaries of result shifts from baseline, worst-case results post-baseline relative to baseline, and results with increase to \geq maximum toxicity grade post-baseline for chemistry, haematology, urinalysis, and immunology as applicable, will also be presented for treatment with GSK3228836 and PegIFN separately, by treatment arm and in total within each treatment period.

GSK3228836 liver chemistry monitoring and stopping event reporting will be summarized and listed. The liver monitoring and stopping criteria are described in the protocol Section 7.1.1.

GSK3228836 haematological monitoring and stopping events will be summarized and listed based on laboratory parameters (platelet count and anti-platelet antibodies). The haematological stopping criteria are described in the protocol Section 7.1.2.

GSK3228836 drug induced kidney injury (renal) monitoring and hold or stopping events will be identified programmatically and will be summarized and listed based on laboratory parameters (ACR, urinalysis red blood cells (RBC), serum creatinine, and eGFR). The kidney injury monitoring and stopping criteria are described in the protocol Section 7.1.3.

Drug induced vascular injury and complement monitoring/stopping event will be summarized and listed based on laboratory parameters (C3, C4, Bb, C5a, hs-CRP, MCP-1, p-ANCA, c-ANCA, eGFR, bilirubin, and platelet count). The drug induced vascular injury and complement monitoring and hold/stopping criteria are described in the protocol Section 7.1.4.

Hold/stopping event profile for GSK3228836 will be provided for any subject who has met hold or stopping criteria specified in protocol Section 7.1. Relevant information will be reported, including baseline characteristics, AEs/SAEs, concomitant medication, medical history/current medical conditions, study treatment administration details, laboratory values, and individual line plots of complement (C3/C4/C5a/Bb), inflammatory markers (hs-CRP/MCP-1), serum creatinine/creatinine clearance or eGFR/ACR, and platelet count.

Haematological (absolute neutrophil count (ANC), platelet count, haemoglobin), ALT elevation (greater than 5 x ULN, greater than 10 X ULN) and psychiatric disorder (C-SVRRS, BDI-II) dose modification and discontinuation guidelines for PegIFN will be summarized and are described in protocol Section 7.2.1, Section 7.2.2, and Section 7.2.3 respectively.

GSK3228836 restart after liver stopping criteria has been met will be summarized based on ALT, bilirubin, and INR, and is described in protocol Section 7.3.

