1.2. Schema

1.3. Schedule of Activities (SoA)

Both treatment arms will use the same Screening Table ([Table 1](#)). Separate tables have been produced for the GSK3228836 treatment period ([Table 2](#) and [Table 3](#)). Both treatment arms will use the same PegIFN Treatment Table ([Table 4](#)), Reassessment of PegIFN Eligibility Tables ([Table 5](#) and [Table 6](#); only required if participant is ineligible to start PegIFN as per [Table 4](#)) and Off Treatment Follow-up Table ([Table 7](#)).

[China specific Schedule of Activities can be found in [Appendix 7: Country-specific requirements](#)]

Instructions that are applicable to all treatment arms include:

- In selected countries/sites, participants will have the option to use a centralised home nursing provider. Only selected visits will have the option to be performed as a home visit, these will include drug administration, blood draws, participant assessments and data collection. The full specifications of the home nursing services will be outlined in the Study Reference Manual (SRM).
- Haematology (platelet count) will be analysed at a local laboratory prior to each GSK3228836 dose. The blood draw can be taken the day before GSK3228836 dosing. Results must be available prior to dosing. Haematology samples will be collected for central laboratory assessments in parallel. After GSK3228836 treatment is completed, haematology is only collected centrally on weeks of clinic visits.
- If a participant is not eligible to start PegIFN, eligibility will be reassessed. If the participant does not become eligible after 13 weeks, PegIFN will not be initiated in order to ensure participants receive at least 12 weeks of PegIFN treatment. Irrespective of the week that a participant starts PegIFN, the final dose will be given on Study Week 48 for Arm 1 and Week 36 for Arm 2 ([Figure 1](#)).
- PegIFN dosing maybe self-administered at home, where local regulations allow at the visits indicated in the SoA ([Table 4](#)).

Figure 1 Schematic of Planned GSK3228836 and PegIFN Dosing Periods and Off Treatment Follow-up Period

[figure not shown]

Table 1 Screening (All Treatment Arms)

ASSESSMENTS	
Informed Consent (obtained any time prior to screening)	X
Inclusion and exclusion criteria	X
Demography	X
Medical history (includes substance usage) and current medical conditions	X
Medication history and concomitant medication review	X
Full physical exam including height and weight	X
Vital signs	X

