7.1.2. GSK3228836 Haematological Stopping Criteria

If a participant develops signs or symptoms of thrombocytopenia, obtain a platelet count (local lab) as soon as possible and hold dosing until the platelet count is confirmed.

If the platelet count is uninterpretable or a decreasing trend is noted below the lower limit of normal (LLN) reference range, re-check the platelet counts as soon as possible (the investigator may, at their discretion, opt to have the participant come to their next scheduled visit OR ask the participant to come earlier than their scheduled visit, as they feel appropriate based on review of the participants clinical presentation and laboratory results). Samples showing platelet clumping should also be repeated.

Participants with platelet values below $75 \times 10^9/L$ will undergo further assessment including, but not necessarily limited to, anti-platelet antibodies. If the participant has a positive anti-platelet antibody, study treatment should be discontinued permanently. Monitor until platelet abnormalities resolve, stabilise, or return to within baseline values.

Table 10 GSK3228836 Haematological Stopping Criteria

Platelet Count	Monitoring	Treatment
75 X 10 ⁹ /L ≤Platelets <100 X 10 ⁹ /L	Monitor weekly, results of local platelet count must be available prior to dosing	Hold treatment until platelets return to ≥100 x10 ⁹ /L
50 X 10 ⁹ /L ≤ Platelets <75 X 10 ⁹ /L	Monitor every 2-3 days until three successive measurements ≥75 x10 ⁹ /L, then weekly Assess anti-platelet antibodies	[if positive for anti-platelet antibodies, study treatment should be discontinued immediately]
<50 x 10 ⁹ /L	Monitor daily until ≥25 x10 ⁹ /L, monitor every 2-3 days until three successive measurements ≥75 x10 ⁹ /L, then weekly until platelets ≥100 x10 ⁹ /L Assess anti-platelet antibodies	Discontinue treatment permanently Glucocorticoids recommended (unless the participant has a medical contraindication to receiving glucocorticoids), and discontinuation of any antiplatelet medicinal products/non-steroidal anti-inflammatory drugs/anticoagulants

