Other Tests	
 Follicle-stimulating hormone and oestradiol (as needed only) Serology (HIV antibody, hepatitis C virus antibody, and hepatitis D virus antibody) Hepatitis B serology (HBsAg, anti-HBsAg, anti-HBeAg, HBV DNA, HBV RNA, HBcrAg) 
 Other laboratory: TSH/T4, prothrombin time (PT), INR, activated partial thromboplastin time (aPTT), Alpha-fetoprotein, ANCA (MPO-ANCA, PR3-ANCA), APRI/Fibrosure, Complement factors C3, C4, C5a, and Bb, hs-CRP, MCP-1, angiopoietin II, PBMC, soluble protein, PAX Gene Urine ACR Optional collections: Genetic sample Viral Sequencing: HBV Genotype, HBV DNA, HBV RNA 
All study-required laboratory assessments will be performed by a central laboratory, with the exception:
 
 Platelet counts for investigator decisions may be drawn at local laboratory
Additional tests listed under safety follow-up processes	
Liver Chemistry Stopping Criteria³
 
 Viral hepatitis serology including: 
 Hepatitis A IgM antibody; Cytomegalovirus IgM antibody; Epstein-Barr viral capsid antigen IgM antibody (or if unavailable, obtain heterophile antibody or monospot testing); Hepatitis E IgM antibody Hepatitis B virus DNA load Hepatitis C virus RNA load Hepatitis D virus antibody PK sample Serum CPK LDH. Fractionated bilirubin, Anti-nuclear antibody, anti-smooth muscle antibody, Type 1 anti-liver kidney microsomal antibodies and quantitative total immunoglobulin G (IgG or gamma globulins). Serum acetaminophen adduct HPLC assay 
Drug Induced Vascular Inflammation and Complement Stopping Criteria
 
 CH50 Factor B level Factor H level sC5b-9

Laboratory Assessments	Parameters
	
Haematological Stopping Criteria
 
 • anti-platelet antibodies 
Drug Induced Kidney Injury Stopping Criteria
 
 • 24-hour urine analysis • renal ultrasound • urine microscopy • serum urea and creatinine • platelets • urgent serum vasculitis screen [including ANCA, ANA, dsDNA, cryoglobulins] • SPEP/ UPEP • complement panel (C3, C4, C5a and Bb)

NOTES:

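### Platelet holds and stops during GSK3228836 dosing are decided on local counts, but SAP 4.5.3.1 admits only central results to the summary of those events, the worst-case platelet summaries and the profile plots

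*SAP*

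**What the plan says.** **Where decisions are made (Protocol).** Section 1.3: "Haematology (platelet count) will be analysed at a local laboratory prior to each GSK3228836 dose". Section 7.1.2, for a participant with signs or symptoms of thrombocytopenia: "obtain a platelet count (local lab) as soon as possible and hold dosing until the platelet count is confirmed". Table 10, in the row for 75 to below 100 x 10^9/L: "Monitor weekly, results of local platelet count must be available prior to dosing". Appendix 2, Table 17, as an exception to central testing: "Platelet counts for investigator decisions may be drawn at local laboratory".

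**The paired sample (Protocol).** Section 1.3 adds: "Haematology samples will be collected for central laboratory assessments in parallel". Appendix 2 repeats this for platelets in the GSK3228836 period and says that, where a local sample is otherwise needed, it is important to take a central one alongside. After GSK3228836 treatment, haematology is collected centrally only.

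**What is tabulated (SAP 4.5.3.1).** "Only central lab data will be used for summary analyses and figures; local lab data will be included in listings, as appropriate". The same section plans toxicity shift tables for haematology, a summary of increases to Grade 3 or higher that names platelets, worst-case and maximum-grade summaries by treatment period, and this: "GSK3228836 haematological monitoring and stopping events will be summarized and listed based on laboratory parameters (platelet count and anti-platelet antibodies"), with the criteria taken from Protocol 7.1.2. It also plans profiles, with platelet line plots, for anyone who met a hold or stopping criterion. None of these outputs is exempted from the central-only rule.

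**The concern.** A table of protocol-defined holds and stops is useful if it shows the events that were acted on. Here the action follows one laboratory's result and the table is built from another's. If the two agree, nothing is lost. If they do not, or if the central result does not exist, a participant whose dose was held under Table 10 may not appear in the summary of Table 10 events. The reverse can also occur: a low central count may be tabulated as an event although the local count led to no action.

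Thrombocytopenia is an adverse event of special interest in both documents, so the laboratory-based event table and the worst-case platelet summaries are outputs that readers will rely on. For worst-case values the direction is known. Adding local counts can only lower a participant's minimum or leave it unchanged, so omitting them can only make it look the same or better.

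**Working it through.** The plan states no figure for this point, so there is none to reproduce. The check sets the texts side by side and counts from the Schedule of Activities.

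**1. Does any SAP rule bring local counts back?**
- *Unscheduled assessments (SAP 6.2.4).* These feed the any-time-on-treatment and any-visit-post-baseline rows. The rule says which visits count. It does not lift the restriction on laboratory source.
- *Duplicate records (SAP 4.5.3.1).* The worst-case choice among records at the same time point works on the data already admitted. Local values are excluded before it applies.
- *Hold/stop profiles (SAP 4.5.3.1).* These report laboratory values and dosing details, but their platelet line plots are figures and so fall under the central-only sentence.
- *Listings.* Local values may appear, where judged appropriate.

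No rule covers a local count that falls in a Table 10 band when the paired central count is absent, uninterpretable or in another band.

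**2. How many local counts have a scheduled central counterpart?**

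Inputs: about 50 participants per arm (Protocol 9.2); 26 and 14 planned GSK3228836 doses (SAP 6.1.5); haematology marked on 24 and 12 of those dosing days, with Days 4 and 11 blank (Protocol Tables 2 and 3).

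| | Arm 1 | Arm 2 | Total |
|---|---|---|---|
| Planned pre-dose local counts | 50 x 26 = 1,300 | 50 x 14 = 700 | 2,000 |
| On days with a haematology mark | 50 x 24 = 1,200 | 50 x 12 = 600 | 1,800 |
| Days 4 and 11 | 100 | 100 | 200 |
| Share of dosing days without a mark | 2/26 = 7.7% | 2/14 = 14.3% | 200/2,000 = 10% |

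So 90% of planned local counts fall on days with scheduled haematology. The other 10% is an upper limit on the scheduled gap, because the general wording on parallel samples may cover Days 4 and 11. The figures assume that every planned dose is given.

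**3. When does a pair fail to protect the event?**
- *Missing central result.* Appendix 2 calls the parallel sample important, but the SAP has no rule for its absence.
- *Uninterpretable central result.* Protocol 7.1.2 itself expects uninterpretable counts and platelet clumping.
- *Discordant pair.* With assumed values, a local count of 96 and a paired central count of 104 (x 10^9/L) is a hold under Table 10 but no event in a central-only table. With the values exchanged, the table shows an event although dosing was not held.

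The documents give no rate for any of the three, so no count of affected events can be derived.

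**The case against.** The strongest reply is that central-only reporting is a normal and defensible choice: one method, one reference range, and a paired central sample for nearly every local count. The protocol's pairing wording is broad, unscheduled results reach the any-visit rows, and a value that meets a stopping criterion must be repeated before withdrawal (Protocol 7), which creates further chances of a central result. Participants who were held or stopped also appear in the profiles, the thrombocytopenia outputs with action taken, the adverse events leading to permanent discontinuation, the reasons for discontinuing treatment, and any local listings. Most of this stands. It limits how often the problem bites, but it does not supply the missing rule.

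Several stronger readings are tempting and are not supported:
- *That 2,000 counts are lost.* They are excluded values, not lost events, and 1,800 fall on days with scheduled haematology.
- *That all urgent and close-interval counts are local.* Only the symptom-driven count and the 75 to below 100 row name a local laboratory. Table 10 names none for the daily and every-2-to-3-day checks.
- *That a permanently stopped participant disappears from safety reporting.* The outputs just listed would still show the stop.
- *That Grade 3 or higher platelets are undercounted by a known amount, or that a platelet nadir table is wrong.* The DAIDS cut-offs are not printed in the documents, and the SAP names no nadir table.
- *That this bears on the Phase 3 decision.* The interim endpoints in SAP 4.7.1 are virologic, and the decision framework is in a charter outside these documents.

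It is also fair to object that simply taking the lower of the two results would admit clumped or unconfirmed counts. The fix therefore has to exclude or flag them.

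**Conclusion.** The point holds in a limited form. Within the GSK3228836 period, the SAP's stated rule keeps the local counts on which platelet decisions rest out of the stopping-event summary, the worst-case and maximum-grade platelet summaries, and the profile plots. This follows from an explicit sentence with no exception and does not depend on reading a silence. An event is lost or misclassified only when the central result is missing, uninterpretable or across a Table 10 threshold from the local one.

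The number of affected events is unknown and may be small. The direction is certain only for comparisons with and without local values: central-only data cannot show a lower worst count, or more threshold crossings, than local and central data together. Routine platelet monitoring after GSK3228836 is not affected, because it is central by design. The conclusion assumes that the central-only sentence governs every summary and figure in SAP 4.5.3.1, as its wording says.

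**What to change.** In SAP 4.5.3.1, for platelets in the GSK3228836 period only:

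1. Derive Section 7.1.2 hold and stop events from both local and central results, including unscheduled samples and excluding results reported as clumped or uninterpretable.
2. Flag each event by source (local, central or both) and as confirmed or unconfirmed on retest.
3. Include the triggering local counts in the platelet plots of the hold/stop profiles.
4. Show the worst post-baseline platelet count and grade with local values added, beside the central-only version.
5. Keep central-only data for by-visit summaries.

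The case for an exception rests on local decision rules that are set out for platelets, so it should not be extended to other parameters. Separately, the protocol's requirement for a local count before each dose and the blank haematology cells on Days 4 and 11 should be reconciled.

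The cost is SAP wording and modest programming. The listings imply that local counts are held in the database, but this should be checked. The downside is between-laboratory variation, which the source flag makes visible.

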10.2. Appendix 2: Clinical Laboratory Tests

The tests detailed in [Table 17](#) will be performed by the central laboratory.

Local laboratory results are required for analysis of platelets during the GSK3228836 dosing period. The blood draw can be taken the day before GSK3228836 dosing. Results must be available prior to dosing. A sample for central analysis is obtained in parallel.

Otherwise, local laboratory results are only required in the event that the central laboratory results are not available in time for either study intervention administration and/or response evaluation. If a local sample is required, it is important that the sample for central analysis is obtained in parallel.

Protocol-specific requirements for inclusion or exclusion of participants are detailed in [Section 5](#) of the protocol.

Additional tests may be performed at any time during the study as determined necessary by the investigator or required by local regulations.

Pregnancy Testing:

Refer to [Section 5.1 Inclusion Criteria](#) for screening pregnancy criteria. Pregnancy testing (urine or serum as required by local regulations) should be conducted according to the [Schedule of Assessments \(Section 1.3\)](#) during the study. Additional serum or urine pregnancy tests may be performed, as determined necessary by the investigator or required by local regulation, to establish the absence of pregnancy at any time during participation in the study.

Table 17 Protocol-Required Safety Laboratory Tests

Laboratory Assessments	Parameters			
Haematology	Platelet Count ¹ RBC Count Haemoglobin Haematocrit	RBC Indices: mean corpuscular volume mean corpuscular haemoglobin	WBC count (with Differential if WBC abnormal): Neutrophils Lymphocytes Monocytes Eosinophils Basophils	
Clinical Chemistry	Blood Urea Nitrogen	Potassium	Aspartate Aminotransferase / Serum Glutamic-Oxaloacetic Transaminase	Total, indirect and direct bilirubin
	Creatinine	Sodium	Alanine Aminotransferase/ Serum Glutamic-Pyruvic Transaminase	Total Protein
	Glucose	Calcium	Alkaline phosphatase	Albumin
Routine Urinalysis	
 • By dipstick • Microscopic examination (if blood or protein is abnormal) 			

Laboratory Assessments	Parameters
Pregnancy testing	
 Highly sensitive urine or serum human chorionic gonadotropin (hCG) pregnancy test (as needed for women of childbearing potential)²

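### Platelet holds during GSK3228836 dosing are decided on local counts, but SAP 4.5.3.1 builds the haematological stopping summary and the profile's platelet plot from central counts only

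*SAP*

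**What the plan says.** **Protocol.** During GSK3228836 dosing the local platelet count is the one acted on.

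- Section 1.3: "Haematology (platelet count) will be analysed at a local laboratory prior to each GSK3228836 dose". The result must be in hand before dosing, and the same bullet asks for a parallel central sample.
- Section 7.1.2, on signs or symptoms of thrombocytopenia: "obtain a platelet count (local lab) as soon as possible and hold dosing until the platelet count is confirmed".
- Section 7.1.2, Table 10, row for 75 to below 100 x 10^9/L: "Monitor weekly, results of local platelet count must be available prior to dosing". Treatment is held until the count is back to at least 100.
- Section 10.2: "Local laboratory results are required for analysis of platelets during the GSK3228836 dosing period". Here too a parallel central sample is requested.

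**SAP 4.5.3.1.** The section opens with the source rule: "Only central lab data will be used for summary analyses and figures; local lab data will be included in listings, as appropriate". Later it says: "GSK3228836 haematological monitoring and stopping events will be summarized and listed based on laboratory parameters (platelet count and anti-platelet antibodies"). No laboratory source is named. It also says: "Hold/stopping event profile for GSK3228836 will be provided for any subject who has met hold or stopping criteria specified in protocol Section 7.1". That profile includes treatment administration details, laboratory values and an individual line plot of platelet count.

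**The concern.** The summary of haematological monitoring and stopping events is where the report would show how often the platelet rules were met. Those rules are applied at the site on one laboratory's count, and the SAP, as written, tabulates them from another's. The two will usually agree. When they do not, the table and the dosing record disagree, and a reader of the report cannot tell why.

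The error can go either way. A participant held on a local count below 100 is not counted if the paired central count is 100 or more, or if there is no usable central count. A participant whose local count was 102 and who was properly dosed is counted as meeting the hold criterion if the central count was 98. The line plot in the profile has the same problem: the count that led to the hold may not be on it.

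Thrombocytopenia is an adverse event of special interest in this trial, so this table will be read closely.

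**Working it through.** The plan states no figure to reproduce. The check is a comparison of texts, followed by an illustration of how far paired counts could disagree.

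**1. Which count decides.** Protocol 1.3 and 10.2 require a local result before each GSK3228836 dose. Section 7.1.2 names the local count both for the symptom-triggered check and in the Table 10 row that carries the hold at 100. The local count is therefore the decision value.

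**2. Which count is tabulated.** The opening sentence of SAP 4.5.3.1 covers all laboratory summaries and figures. The haematological event summary is in the same section, is based on platelet count, and has no exception. A line plot is a figure, so the profile's platelet plot falls under the same rule.

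**3. When the two differ.** With the parallel sample taken and readable, the two sources differ only when the counts fall on opposite sides of a threshold. Without a usable central sample, the local count stands alone. Section 7.1.2 itself anticipates uninterpretable and clumped samples.

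**4. Illustration.** The documents give no between-laboratory variability. Assume that, given a local count L, the paired central count is Normal with mean L and standard deviation CV x L, with CV between 3% and 10%.

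Hold made on the local count but not seen centrally: P(central >= 100) = 1 - Phi((100 - L)/(CV x L)). For L = 95 and CV 3%, (100 - 95)/(0.03 x 95) = 1.754, which gives 0.040.

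| Local count L | CV 3% | CV 5% | CV 10% |
|---|---|---|---|
| 90 | 0.0% | 1.3% | 13.3% |
| 95 | 4.0% | 14.6% | 29.9% |
| 98 | 24.8% | 34.2% | 41.9% |

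No hold on the local count but criterion met centrally: P(central < 100) = Phi((100 - L)/(CV x L)). For L = 102 the arguments are -2/3.06 = -0.654, -2/5.10 = -0.392 and -2/10.2 = -0.196, which give 25.7%, 34.8% and 42.2%.

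**5. From sample to participant.** These are chances for one pair of samples. A held participant is missed only if every central count in the episode reads 100 or more. If L stays at 95 over two visits and the pairs disagree independently, the chances become 0.040^2 = 0.2%, 0.146^2 = 2.1% and 0.299^2 = 8.9%. A consistent offset between the two laboratories would break the independence and make the reduction smaller.

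Disagreement matters only close to a threshold, and it falls quickly once an episode spans more than one central sample.

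**The case against.** The best defence is the parallel central sample. Protocol 1.3 and 10.2 both ask for it, and note 1 to Table 17 again calls for local and central platelet collection on treatment. If that is followed, nearly every local count has a central partner. Entry also excludes platelets below 140 x 10^9/L, so a participant must fall some way before a threshold comes into play, and an abnormality that meets a stopping criterion is to be repeated before withdrawal. Haematological events are listed as well as summarised, local results go to listings as appropriate, and thrombocytopenia is reported separately as an event of special interest, including action taken. All of this stands, and it is why the effect is likely to be small. It does not supply the missing exception in 4.5.3.1.

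Four stronger readings are tempting, and the documents do not support them.

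- *A fixed share of pre-dose checks has no central count, because Tables 2 and 3 mark no haematology on dosing Days 4 and 11.* The bullet that requires the local count also requires the parallel central one. If the text governs, both are taken; if the table governs, neither is scheduled. This is an ambiguity in the schedule, not a known gap in central data.
- *The closely spaced re-checks during a platelet fall are local only.* Section 7.1.2 does not mention a central partner for them, but 10.2 asks for one during GSK3228836 dosing.
- *Central-only grade tables must understate the fall in platelets.* Counts vary in both directions, so a central minimum can also lie below the true lowest level. Taking the lower of two laboratories would produce more false low values.
- *Participants held on a local count are denied a profile.* Entry depends on having met a Section 7.1 criterion, and a local count below 100 does meet one. Only the plot is clearly caught by the central-only rule.

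**Conclusion.** The concern holds, for one table and one plot. Read as written, SAP 4.5.3.1 reports the platelet monitoring and stopping rules from a laboratory other than the one on which holds are decided, with no exception. The summary can therefore omit a hold that was made or count one that was not, and the profile plot can leave out the count that led to the hold.

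The number of participants affected cannot be estimated: the documents give no rate of low platelet counts and no rate of disagreement between laboratories. The percentages in the working rest on an assumed CV and apply only to counts near 100. The effect is probably small.

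The point is limited to the GSK3228836 dosing period. By-visit and grade summaries from central data are a reasonable choice. Listings, adverse event and special-interest tables, and the primary endpoint are untouched.

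**What to change.** Keep central-only data for by-visit and grade summaries. Add to SAP 4.5.3.1 that, during GSK3228836 dosing:

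1. haematological monitoring, hold and stopping events are derived from both local and central platelet counts, with the source of each qualifying count shown;
2. any participant who meets a criterion on either count receives a hold/stopping profile;
3. local counts are plotted in the profile and flagged as local.

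The cost is one or two sentences and modest programming. Local results are already planned for listings, so no new data are collected. The drawback is that one table mixes laboratories; showing the source deals with that and lets the reader see where the two disagree. If the sponsor already intends to use local counts here, the same text records it.
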